#### 8.2.4 Time Period and Frequency for Event Assessment and Follow Up

AEs will be followed up until stabilized or resolution from study entry through end of study.

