Assessment	Screening &	Baseline	nent recording ar Intervention	Follow-Up	Follow-Up	Follow-Up
	Randomization Visit 0 Days -5 to 0	Assessments Visit 1 Days 1-5 (+/-4 days)	Period Visits 2-30 a For 3, 4.5, or 6 weeks (+/- 3 days)	Visit 1 1-week post intervention b (+/- 3 days) c	Visit 2 3-month post intervention b (+/- 1 week) c	Visit 3 6-month post intervention b (+/- 1 week) c
Informed consent	Χ					
Review of eligibility criteria and randomization	Х					
Concomitant Aphasia Treatment				X		Х
Assess New Adverse Events			X	Χ		
Verbs per Minute (VPM)		Χ		Χ	X	X
Gathering of individual demographic and baseline characteristics (Table 3)		X				
NIH Stroke Scale (NIHSS)	X					
Western Aphasia Battery- Revised (WAB-R)	X d, e			Х	Х	Х
Quality of life assessment - Stroke and Aphasia Quality of Life (SAQOL-39g)		Х		X	X	X
Charlson Comorbidity Index		Χ				
Communicative Effectiveness Index (CETI)		X		X	X	
Lexical Orthography Familiarity Test (LOFT)		Х				
Modified Epworth Sleepiness Scale (ESS)						
Apraxia of Speech Rating Scale 3.0 (ASRS 3.0)	X d			X	Х	
Pyramids and Palm Trees Test (PPTT)		Х				
Matrix Reasoning - Wechsler Adult Intelligence Scale, Third Edition (WAIS-III)		Х				
Vertical Numerical Rating Scale-Face Rating Scale for post-stroke fatigue (NRS- FRS)		Х				
Modified Philadelphia Repetition Test (PRT)		X		X	Х	
Modified Philadelphia Naming Test (PNT)		X		X	Х	
Stroke Aphasic Depression Questionnaire (SADQ-10)		X				
MRI					(opt	ional)

Footnote: aNumber of visits depend on randomized arm. bFollow-up assessments can be completed over 1-5 days. cDefinitions for the follow-up visit target date and window provided in Table 2. dRepeat WAB-R/ASRS 3.0 measures prior to intervention if initiation of intervention period occurs >15 days post randomization. eUse of WAB-R scores obtained for other purposes, administered within 120-days before randomization, is allowed.

Note: In the event of technological difficulties, readministration of baseline or follow-up testing will be conducted within study timeline constraints to maintain the integrity of data collection.

Table 2. Follow-Up Visit Target and Visit Windows in Days						
Randomization	Follow-Up	Follow-Up	Follow Up			
Assignment	Visit 1	Visit 2	Visit 3			

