# 1.3.3.1 Assessment of Adverse Events

We will ask the participant to report adverse events (AEs) as they occur and will routinely ask the participant at the end of each week of intervention. We will also call each participant in the no SET group weekly to assess AEs. See section 8.2 for more information regarding the definition and classification of AE and guidelines for reporting events.

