# 4.0 Study Design

# 4.1 Overall Design

Approach: We propose a prospective, controlled, randomized, assessor-blinded, phase II clinical trial (n=80) entitled Speech entrainment for Aphasia Recovery (SpARc). The goals of the trial are to evaluate SET in comparison with no SET (control), and to determine SET's best dose (duration of treatment in weeks). SET and assessments will be delivered via telehealth. We will enroll 80 participants and randomly assign them 1:1:1:1 to one of the 4 groups (A, B, C, D):

- A SET for 3 weeks (15 days, 1 hour daily, 5 x week)
- B SET for 4.5 weeks (22 days, 1 hour daily, 5 x week)
- C SET for 6 weeks (30 days, 1 hour daily, 5 x week)
- D No SET for 6 weeks (control condition)

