#### 9.4.6 Safety Analyses

Monitoring Plan for Worsening in the Primary Outcome: If SET leads to substantially worse outcome than the no SET arm, early stopping may be considered. The unblinded statistician will fit the primary analysis model semi-annually in order to compare VPM between the combined SET durations versus No SET (one-sided  $\alpha$ =0.025). As part of this analysis, outliers will be explored to ensure that the results are not driven by a specific individual. Should the null hypothesis be rejected, an investigation of dose response among the SET arms based on qualitative evaluation (i.e. not statistical) when ordered in terms of dose level will occur. Should a dose response relationship be detected, the unblinded statistician will bring this to the attention of the DSMB and investigators.

All AEs and SAEs are summarized by preferred term according to the Medical Dictionary for Regulatory Activities (MedDRA) adverse reaction dictionary in terms of frequency of the event, number of subjects having the event. For the Closed DSMB report, severity, and relatedness to the treatment will also be shown by treatment group.

At the end of the trial, the cumulative incidences of the specific SAEs related to treatment, as well as all SAEs, will be compared across groups.

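### Scheduled enquiry for new adverse events stops at the 1-week visit, so the planned SAE comparison across arms has unequal observation windows and no stated time horizon

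*Protocol*

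**What the plan says.** **Scheduled enquiry.** In the protocol's Table 1, the row "Assess New Adverse Events" is marked for the intervention period and Follow-Up Visit 1 only. Nothing is marked at the 3-month or 6-month visit, although efficacy measures such as VPM and SAQOL-39g are marked there. Section 1.3.3.1 agrees on routine questioning: staff "will routinely ask the participant at the end of each week of intervention", and for control, "We will also call each participant in the no SET group weekly to assess AEs". Section 4.3.2 places the control calls within the six no-SET weeks.

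**Unprompted reporting.** Section 1.3.3.1 also says "We will ask the participant to report adverse events (AEs) as they occur", with no stop date. Section 8.2.3 requires SAEs to be charted and reported, again with no cut-off. It requires other AEs to be reported only if they are related to the intervention.

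**Period.** Section 8.2.4, whose heading covers both event assessment and follow-up, consists of one sentence: "AEs will be followed up until stabilized or resolution from study entry through end of study".

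**Analysis.** Protocol 9.4.6 describes the final safety comparison in these words: "the cumulative incidences of the specific SAEs related to treatment, as well as all SAEs, will be compared across groups". SAP section 12 has the same sentence. Neither gives a time horizon, a common window or an exposure adjustment.

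**The concern.** A cumulative incidence has meaning only with a stated period of observation. Here the period of active questioning is tied to the length of treatment, so it differs by arm. If two arms have the same underlying SAE rate, the arm questioned for longer is expected to show more events. Within the SET arms this would resemble a dose gradient, and the 3-week and 4.5-week arms would look safer than control for no clinical reason.

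After the 1-week visit, no scheduled contact includes a question about new events. Capture then depends on participants volunteering them, and all participants were selected for non-fluent aphasia. Section 4.1.1 goes to some trouble to align the behavioural assessments across arms so that the data can be compared. The safety data have no such alignment.

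At stake are the end-of-trial SAE comparison, the by-arm safety tables for the DSMB that draw on the same capture, and knowledge of events between 1 week and 6 months.

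**Working it through.** **Inputs.** Treatment lasts 3, 4.5 and 6 weeks in A, B and C, and the control period is 6 weeks (protocol 4.1). In the SET arms, follow-up targets are 7, 90 and 180 days after the last session. In control they are 54, 137 and 227 days after randomization (Table 2). There are 20 participants per arm. The documents give no background SAE rate, so I assume a constant, equal rate and show a range.

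**Reproducing the plan's figures.** Control targets: 5 days of baseline + 42 days + 7, 90 or 180 days = 54, 137 and 227 days, as stated. Treatment plus 180 days (25.7 weeks) gives 28.7 weeks in A and 31.7 weeks in C, in line with the stated 28 to 31 weeks of participation.

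**Reading 1: capture ends with scheduled enquiry.** Window = treatment weeks + 1.
- A: 3 + 1 = 4
- B: 4.5 + 1 = 5.5
- C: 6 + 1 = 7
- D: 6 + 1 = 7

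C/A = 7/4 = 1.75. Counting calendar days from a Monday start gives 26, 37 and 47 days for A, B and C, so C/A = 47/26 = 1.81, the same pattern.

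**Reading 2: unprompted capture is complete to 6 months.** Window = treatment weeks + 25.7, giving 28.7, 30.2, 31.7 and 31.7 weeks. C/A = 31.7/28.7 = 1.10.

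**Between the readings.** The time from the 1-week to the 6-month visit is the same in every arm: 180 − 7 = 173 days, or 24.7 weeks. If a fraction p of events in that time is captured, equally in all arms, the expected-event ratio is

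C/A = (7 + 24.7p) / (4 + 24.7p)

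This is 1.75 at p = 0, about 1.18 at p = 0.5, and 1.10 at p = 1. C and A differ by three weeks of observation throughout.

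**Size under no treatment effect.** Cumulative incidence = 1 − exp(−rate × window), and expected participants with an event = 20 × incidence. Reading 1 gives:

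| Assumed rate per week | A | B | C and D | D − A, participants |
|---|---|---|---|---|
| 0.25% | 1.0% | 1.4% | 1.7% | 0.35 − 0.20 = 0.15 |
| 0.5% | 2.0% | 2.7% | 3.4% | 0.69 − 0.40 = 0.29 |
| 1% | 3.9% | 5.4% | 6.8% | 1.35 − 0.78 = 0.57 |
| 2% | 7.7% | 10.4% | 13.1% | 2.61 − 1.54 = 1.07 |

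Under reading 2 the D − A difference is 5.44 − 4.99 = 0.45 participants at 1% per week and 9.39 − 8.74 = 0.65 at 2%.

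**The case against.** The strongest reply is that scheduled questioning about AEs does not define SAE capture, and the planned comparison is of SAEs only. Participants are asked to report events as they happen, SAE reporting has no cut-off, and section 8.2.4 can fairly be read as running to the end of the study. On that reading the ratio is 1.10, not 1.75. This stands in part. Nothing in the documents says SAE capture stops at the 1-week visit, so 1.75 is an upper bound and not an estimate. But nothing says new events are sought after that visit either, and complete unprompted capture in this population should not be taken for granted.

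Nor are all the marks in Table 1 beyond doubt. The concomitant-treatment row has no mark at Follow-Up Visit 2, although Table 5 divides its recording at the 3-month visit. The Epworth row is empty, although section 1.3.2 lists that scale at baseline. The point should therefore not rest on Table 1 alone. Section 1.3.3.1 independently ties routine questioning to the intervention weeks.

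Three further replies stand. For treatment-related SAEs, longer time on treatment is part of the dose, so the artefact mainly concerns the comparison of all SAEs. The comparison has no test or threshold. And concentrating active questioning around treatment is a defensible choice for a low-risk behavioural intervention. None of these supplies the missing time horizon.

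**Conclusion.** The point holds in a limited form. Active enquiry covers about 4, 5.5, 7 and 7 weeks, section 8.2.4 does not say whether new events are sought after that, and the SAE comparison has neither a common window nor a person-time denominator. At equal background rates, arms A and B can appear safer than C and D. The expected-event ratio of C to A is between about 1.10 and 1.75, and the documents do not say where in that range it falls. In participants, the distortion is about one per arm or fewer at rates up to 2% per week. This rests on a constant rate equal in all arms, complete capture while questioning is active, and rates that are my assumptions.

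A reader might infer that safety is confounded with dose across the whole trial, that SET would be made to look worse than control, or that the choice of best duration is biased. The documents support none of these:
- C and D have the same 7-week window, so their comparison is not distorted by window length, and no SET arm is observed for longer than control.
- The safety objective in section 3.0 concerns SET as such, not safety by dose.
- The selection rule (protocol 9.4.4, SAP 9) uses VPM and session participation. Adverse events do not enter it.

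This is an inexpensive improvement worth making, not a threat to the primary result.

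**What to change.** 1. **Protocol Table 1 and section 8.2.4.** Mark "Assess New Adverse Events" at Follow-Up Visits 2 and 3 in all four arms. In 8.2.4, state one ascertainment period for new AEs and SAEs, separately from how long known events are followed. Align section 1.3.3.1 with it.
2. **Protocol 9.4.6 and SAP 12.** Compare SAEs over one common window counted from the same origin in every arm, for example randomization, or report events per person-week. A common window has the advantage of not needing a constant rate. It should close no later than arm A's final visit, whose target is about 5 + 21 + 180 = 206 days after randomization, less an allowance for the visit window.

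Adding the visits without the second change would still leave the ratio of about 1.10, so both are needed. The cost is a few minutes of questions at visits that already take place, and a small amount of added analysis described in a sentence in each document. No extra visits or staff are required.

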#### 9.0 Statistical Considerations

#### 9.1 Statistical Hypotheses

• Primary Endpoint:

VPM at 3 months post treatment

We hypothesize that, compared to participants who receive control, participants who receive SET for 3, 4.5, or 6 weeks for aphasia will have improved VPM at 3 months and that there is an optimal duration of SET therapy. However, this study was not designed to formally test

SET versus control. This study represents the first step in a series of studies which will ultimately test this hypothesis; however, for this study no formal hypothesis tests are planned. The primary analyses will be descriptive statistics of VPM at 3 months and will estimate the effect size of each SET duration and the pooled SET durations versus control adjusting for baseline.

#### 9.2 Sample Size Determination

#### 9.2.1 Sample Size Considerations for Comparison with Control group

This study is not powered to detect statistically significant differences between the chosen SET dose and the control group. The sample size was determined by administrative reasons. This will be the focus of a later and dedicated comparison study once the best dose has been defined.

#### 9.2.2 Sample Size Considerations for Effect Size of SET versus Control group

For each treatment group versus control, we will estimate the standardized mean difference (effect size). The criterion needed to accept any duration is that the effect size is at least 0.36 (a "small" effect size). The rationale for this criterion is that if the pooled standard deviation estimate is large, because of the small sample size, then the effect size may be smaller than expected. We consider a 20% improvement from control to be the the minimum clinically important difference (MCID). This corresponds to an increase of 1 VPM based on our pilot data (20% of 5 VPM). Given the MCID and the common SD of change in the VPM estimate from pilot data (SD=2), the expected effect size is 0.5. However, with n=20 per group, the observed SD may be as large as 2.74 based on the one-sided upper 95% confidence interval for the common SD; thus, the observed effect size may be only 0.36.

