It remains undefined for whom, why, and how much SET can be of benefit. It is very likely that, within the category of non-fluent aphasia, individuals with different aphasia types (and, thus, with different levels of repetition and comprehension impairment) may benefit differently. For this reason, this study will focus on evaluating whether SET is indeed associated with consistent results, and whether the improvement achieved with SET is comparable with an effect size reported in the literature for conventional speech therapy. If SET is indeed determined to be associated with therapeutic benefits, a "go" decision will be made for a future definitive clinical trial comparing SET with other forms of therapy. During this future study, it will be paramount to determine the individual determinants of therapy success, not only to better inform clinicians, but also to evaluate the mechanisms associated with differential responses from SET versus other forms of therapy.

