##### *Sample Size Considerations for Effect Size of SET versus Control group*

For each treatment group versus control we will estimate the standardized mean difference (effect size). The criteria needed to accept any duration is that the effect size is at least 0.36 (a “small” effect size). The rationale for this criteria is that if the pooled standard deviation estimate is large, because of the small sample size, then the effect size may be smaller than expected. We consider a 20% improvement from control to be the MCID. This corresponds to a 1 point improvement in VPM (5x20%=1). Given the MCID=1 and the common SD of change in VPM estimate from pilot data of 2, we expect the effect size to be  $\frac{1}{2}=0.5$ . However, with  $n=20$  per group, observed SD may be as large as 2.74 (i.e. a one-sided upper 95% confidence interval for  $SD=2$  is 2.74), thus the observed effect size may be only  $1/2.74=0.36$ .

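### The 0.36 acceptance bar allows for chance in the SD but not in the mean difference, so on the plan's own inputs (unadjusted) an MCID-sized duration misses it about one time in three

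*Protocol*

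**What the plan says.** Protocol 9.2.2 and the matching part of SAP 4 make an observed standardized mean difference against control of at least 0.36 a condition for accepting a duration (Protocol: "The criterion needed to accept any duration is that the effect size is at least 0.36"; SAP: "The criteria needed to accept any duration is that the effect size is at least 0.36").

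The reason given concerns the denominator only: "if the pooled standard deviation estimate is large, because of the small sample size, then the effect size may be smaller than expected". The MCID is 1 VPM. With "the common SD of change in the VPM estimate from pilot data (SD=2), the expected effect size is 0.5", the plan then argues that "with n=20 per group, the observed SD may be as large as 2.74 based on the one-sided upper 95% confidence interval". The SAP prints the last step, 1/2.74, and concludes "thus the observed effect size may be only" 0.36. Neither document mentions sampling error in the mean difference, and neither says how often the bar would pass or fail a duration.

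The selection rule (Protocol 9.4.4, SAP 9) uses the highest effect size and at least 80% average participation. It does not repeat 0.36.

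**The concern.** The derivation presents 0.36 as how low the observed effect size might fall when the true effect is the MCID. An observed effect size is a ratio, and at this sample size nearly all of its chance variation comes from the numerator, which the derivation freezes. The bar therefore lacks the property that its rationale gives it.

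No p-values are planned for duration against control, so 0.36 is the one numeric efficacy threshold stated for a duration. If its error rates are not known, a duration with a worthwhile effect could be set aside, or an ineffective one carried into the definitive trial, on a rationale that understates the play of chance.

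**Working it through.** **Inputs.** n = 20 per arm, SD of change 2 VPM, MCID 1 VPM, bar 0.36 (Protocol 9.2.2, SAP 4). Three durations share one control, allocated 1:1:1:1 (Protocol 4.1). No dropout rate is given, and withdrawals are not replaced (Protocol 7.1).

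**1. The plan's own figure.** Upper SD limit = 2 × √(df/χ²₀.₀₅,df). With 19 df this is 2.741, and 1/2.741 = 0.365, which matches 2.74 and 0.36. With 38 df (two pooled arms) the limit is 2.47 and the bar would be 0.40. The argument below does not depend on that choice.

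**2. What the SD-only argument implies.** With the mean difference fixed at 1, the bar is missed when the observed SD exceeds 1/0.36 = 2.78. Given a true SD of 2, P(χ² > df × (2.78/2)²) = 0.9% at 19 df and 0.05% at 38 df. (This is below 5% because 2.74 is a confidence limit for the true SD. The 95th percentile of the observed SD is 2.52 at 19 df.)

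**3. Size of the omitted part.** SE of the mean difference = 2 × √(2/20) = 0.632 VPM, or 0.316 in effect-size units. The gap between 0.50 and 0.36 is 0.14, less than half of one SE. At a true effect of 0.5 the variance of the observed effect size is 0.109. Chance in the SD alone gives 0.0037, or about 3%.

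**4. Unadjusted operating characteristics.** d × √(n/2) follows a noncentral t with 38 df and noncentrality δ × √10. The bar sits at 0.36 × 3.162 = 1.138.

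| True effect | Clears 0.36 | Misses 0.36 |
|---|---|---|
| 0.5 (MCID) | 67.2% | 32.8% |
| 0.25 | 36.8% | 63.2% |
| 0 | 13.1% | 86.9% |

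Normal check at the MCID: Φ((0.36 − 0.50) × 3.162) = Φ(−0.443) = 32.9%. The 5th percentile of the observed effect size at δ = 0.5 is −0.02.

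**5. At least one of three null durations clears the bar.** In 400,000 simulated trials with a shared control the rate is 27.4% (SD from the pair of arms), 27.0% (four-arm SD) or 27.8% (control SD). Treating the comparisons as independent would wrongly give 34.4%.

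**6. Covariate adjustment.** The primary model adjusts for site, severity, baseline VPM and age. The documents do not say which SD standardizes the difference. R² is assumed:

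| R² | Standardizing SD | MCID missed | Any of three null clears |
|---|---|---|---|
| 0.1 | raw change | 32.0% | 24.9% |
| 0.1 | residual | 29.9% | 27.1% |
| 0.3 | raw change | 29.8% | 19.7% |
| 0.3 | residual | 22.6% | 27.1% |

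The pilot SDs in Protocol 4.3.1 (3.9 before, 4.8 after, 1.98 for the difference) give a covariance of baseline with change of (4.8² − 3.9² − 1.98²)/2 = 1.955. So baseline VPM alone explains about (1.955/(3.9 × 1.98))² = 6% of the variance of change. The share due to the other covariates is unknown.

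**7. Attrition (assumed 18 or 17 evaluable per arm, unadjusted).** MCID missed 33.6-34.0%; any of three null clears 29.7-30.9%.

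**8. Bar at 0.40 (38 df).** An MCID-sized duration clears it 62% of the time, so changing the degrees of freedom does not cure the problem.

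**The case against.** The strongest reply is that the trial does not claim inferential force for this bar. Protocol 9.1, 9.2.1 and 9.4.2 and their SAP counterparts say that no formal tests are planned, that the study is not powered against control, that the sample size was administrative, and that a dedicated comparison will follow. A 95% CI for each raw difference is planned, as is a pooled SET-versus-control estimate. Much of the remedy is therefore already in place.

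This stands in part. Those statements disclaim significance testing. They do not say how often the acceptance bar errs, and they leave its derivation uncorrected. The planned CIs are for the raw difference, not for the standardized effect that is compared with 0.36.

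The reply is right against three stronger readings that a reader might infer:

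- **That 0.36 alone decides acceptance.** It is worded as a needed condition. Selection also turns on the highest effect size and 80% participation, so the rates above describe one condition and not the whole rule.
- **That it drives the go decision.** Protocol 2.2.4 conditions that decision in general terms ("If SET is indeed determined to be associated with therapeutic benefits") and does not cite 0.36.
- **That the plan claims durations below 0.36 are ruled out with 95% confidence.** It does not. The 95% belongs to the SD limit.

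It is also fair that the unadjusted 33% and 27% are not the exact rates of the planned model.

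**Conclusion.** The concern holds as a defect in the stated rationale for a decision threshold. On the documents' inputs, unadjusted and without dropout, a duration with exactly the MCID effect misses 0.36 about 33% of the time rather than under 1%. A null duration clears it about 13% of the time, and at least one of three about 27%. With covariates explaining an assumed 10-30% of variance, the MCID miss rate is roughly 23-32% and the any-of-three rate 20-27%, depending on the unstated standardizing SD. An assumed loss to 17-18 per arm raises the unadjusted figures to about 34% and 30-31%.

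The error rates stay large across these ranges, but a flat claim of more than one in four for the null case would go too far: it fails under modest adjustment with a raw-SD denominator. Nothing here shows that 0.36 is the wrong number. It shows that falling on either side of it says little about a single duration.

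**What to change.** In Protocol 9.2.2 and SAP 4:

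- Replace the statement that chance could bring the observed effect size down only to 0.36 with a statement that 0.36 is a pragmatic screening threshold. The bar then keeps a stated basis and its value need not change.
- Give the operating characteristics above, labelled with their assumptions (20 per arm, SD 2, unadjusted, no dropout), together with the adjusted and attrition ranges. Name the SD that will standardize the adjusted difference.
- State that missing the bar does not show a duration to be ineffective, and that clearing it does not show benefit.
- Report each standardized effect size with its 95% CI beside the bar. Unadjusted, the half-width at an effect of 0.5 is about 1.96 × √(0.1 + 0.25/76) = 0.63.
- Use the already planned pooled SET-versus-control estimate, with its CI, as the evidence on whether SET works.

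The cost is a paragraph in each document and one table column. The stated reassurance becomes less favourable. No extra participants are needed.

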#### 9.4.2 Analysis of the Primary Endpoint

The primary outcome is VPM, which is a continuous value greater than 0. It is collected at baseline, 1 week, 3, and 6 months post treatment period. The primary analysis will calculate the change from baseline. The statistical model will be a repeated measures model (SAS\* MIXED procedure with REPEATED subcommand). The model will include the following fixed effects: categorical visit (1 week, 3, and 6 months post treatment period) by treatment group (class variable) interaction, site, baseline aphasia severity score, baseline VPM and age. The estimated difference (95% confidence intervals) in change between each SET duration group and control

group will be reported as the primary analysis. The standardized mean difference for each SET duration versus control will also be reported and will be used to select the best dose of SET. Since this study is not powered for direct comparison with control, no p-values will be reported. Estimates of the change at 1-week and 6 months obtained from this model are exploratory analyses. Additionally, as an exploratory analysis, the combined SET duration versus control comparison will be tested at a two-sided alpha of 0.05.

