#### 9.4.4 Pre-specified rule to select best SET duration

- 1- Highest standardized mean difference (effect size) in VPM from baseline to three months post treatment;
- 2- Adequate tolerability: group average participation in at least 80% of the treatment sessions; We will select the duration associated with the highest group average VPM at 3 months post treatment, but also had adequate tolerability.

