## 7. ANALYSIS OF THE PRIMARY ENDPOINT

The primary outcome is VPM which is a continuous value greater than 0. It is collected at baseline and after 3 months post treatment. The primary analysis will calculate the change in average VPM (from the Narrative Story Telling Task and Procedural Story Telling Task) from baseline. The statistical model will be a repeated measures model (SAS® MIXED procedure with REPEATED subcommand). The model will include the following fixed effects: categorical visit (1 week, 3, and 6 months post treatment period) by treatment group (class variable) interaction, site, baseline aphasia severity score (centrally scored), baseline VPM and age. The estimated difference (95% confidence intervals) in change between each SET duration group and control group will be reported. The standardized mean difference for each SET duration versus control will be used to select the best dose of SET. Since this study is not powered for direct comparison with control, no p-values will be reported.

Empirical robust sandwich estimators will be used to account for the randomization procedure in order to appropriately estimate the marginal treatment effect. The unstructured covariance matrix for repeated observations within subjects will be used. In case the model will not converge, the maximum-likelihood (ML) estimation method will be used instead of the default restricted ML (REML). If the model still does not converge, a simpler covariance structures with less parameters will be used, according to the following order: heterogeneous autoregressive(1) (ARH(1)), heterogeneous compound symmetry (CSH), autoregressive(1) (AR(1)), and compound symmetry (CS). The estimated means at the 3 month post visit of the change from baseline in VPM will be compared for the SET 3 week group versus control, SET 4.5 week versus control, SET 6 week versus control, and the combined SET durations versus control. The SAS code for this analysis is as follows:

```
PROC MIXED EMPIRICAL;
  CLASS SUBJID ARM VISIT CENTER;
  MODEL CHANGE=ARM|VISIT CENTER BASE_WABAQ BASE_VPM AGE;
  REPEATED VISITNUM / TYPE=UN SUBJECT=SUBJID R RCORR;
  LSMEANS ARM*VISIT/ cl;
RUN;
```

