## **9. PRE-SPECIFIED RULE TO SELECT BEST SET DURATION**

- 1- Highest standardized mean difference (effect size) in VPM from baseline to three months post treatment
- 2- Adequate tolerability: group average participation in at least 80% of the treatment sessions

We will select the duration associated with the highest group average VPM at 3 months post treatment, but also had adequate tolerability.

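### The 0.36 acceptance bar rests on an SD limit that Protocol 9.2.2 assigns to the common SD, but 2.74 is the limit for one arm of 20; for the two-arm pooled SD the same method gives 2.47 and 0.40

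*Protocol*

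**What the plan says.** Protocol 9.2.2 sets an effect-size condition on every SET duration: "The criterion needed to accept any duration is that the effect size is at least 0.36". The effect size is the standardized mean difference between each SET arm and control. The reason given for a lenient bar is what happens "if the pooled standard deviation estimate is large". The section takes a common SD of change of 2 from the pilot and an MCID of 1 VPM, which gives an expected effect size of 0.5. It then states that with 20 per group "the observed SD may be as large as 2.74 based on the one-sided upper 95% confidence interval for the common SD", so the observed effect size may be only 0.36.

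SAP 4 gives the same rationale and the same two figures ("observed SD may be as large as 2.74"). It describes 2.74 as the limit for an SD of 2 and does not call it the limit for the common SD. Neither document states degrees of freedom.

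On use of the effect size, Protocol 9.4.2 says "The standardized mean difference for each SET duration versus control will also be reported" and SAP 7 says "The standardized mean difference for each SET duration versus control will be used to select the best dose of SET". Neither defines the SD in the denominator. The selection rule (Protocol 9.4.4, SAP 9) ranks durations by "Highest standardized mean difference (effect size) in VPM from baseline to three months post treatment" and adds "Adequate tolerability: group average participation in at least 80% of the treatment sessions". It does not mention 0.36.

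**The concern.** A two-group effect size standardized by a pooled SD has the degrees of freedom of both groups, 38 with 20 per arm. A limit quoted for that SD should use 38 df, yet 2.74 looks too wide for it. The sentence also changes quantity: a confidence limit describes how large the true SD could be given an estimate, whereas the text uses it to say how large the observed SD could turn out to be.

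This matters because dose selection is the primary objective and 0.36 is the only numerical effect-size condition for accepting a duration. If its justification belongs to a different SD from the one named, the bar is more lenient than its own rationale supports. With the denominator undefined in Protocol 9.4.2 and SAP 7, the bar and the estimate compared with it could also rest on different SDs.

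**Working it through.** **Inputs.** SD of change 2 (Protocol 9.2.2, SAP 4; the pilot value in Protocol 4.3.1 is 1.98 from 15 people). MCID 1 VPM. 20 per group in four arms. One-sided upper 95% limit.

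**Formula.** Upper limit for an SD: s × √(df / χ²(0.05, df)), with s = 2. Implied bar: 1 / upper limit.

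**The plan's figure.** One arm of 20, df = 19, χ²(0.05, 19) = 10.117: 2 × √(19 / 10.117) = 2.741, and 1 / 2.741 = 0.365. This reproduces 2.74 and 0.36.

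**The SD that Protocol 9.2.2 describes.**
- SET arm plus control, df = 38, χ²(0.05, 38) = 24.884: 2 × √(38 / 24.884) = 2.47, and 1 / 2.47 = 0.40.
- All four arms pooled, df = 76, χ²(0.05, 76) = 56.920: 2 × √(76 / 56.920) = 2.31, and 1 / 2.31 = 0.43.

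At 38 df a two-sided 95% interval gives 2.58, and using n instead of df in the numerator gives 2.54 (one-sided) or 2.64 (two-sided). None reaches 2.74. At 38 df, 2.74 would be a one-sided limit of about 99.2%.

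**Observed versus true SD.** If the true SD is 2, the 95th percentile of the observed 38-df SD is 2 × √(χ²(0.95, 38) / 38) = 2 × √(53.384 / 38) = 2.37. The chance that the observed SD exceeds 2.74 is about 0.09% at 38 df (1.2% at 19 df).

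**What the difference does.** Assume unadjusted change, true SD 2, 20 per arm, no dropout, and the SD pooled over the SET arm and control. A bar d corresponds to t = d × √(20/2): 1.138 for 0.36 and 1.265 for 0.40. A dose at the MCID has non-centrality 0.5 × √10 = 1.581. Single-dose figures are exact (central and non-central t, 38 df). The three-dose figure is from 400,000 simulated trials with a shared control.

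| Bar | One ineffective dose passes | At least one of three ineffective doses passes | A dose at the MCID passes |
|---|---|---|---|
| 0.36 | 13.1% | about 27% | 67.2% |
| 0.40 | 10.7% | about 23% | 62.6% |

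These figures are for the effect-size condition alone, without the 80% participation condition.

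**The case against.** The strongest reply is that the printed inputs do yield the printed result: SD 2, 20 per group, one-sided 95% and MCID 1 give 2.74 and 0.36 at 19 df. On this view, common means an SD assumed equal across arms, with its precision taken from one arm. The pilot SD is itself called common although the pilot had a single group, and SAP 4's wording fits this reading. That much stands: the arithmetic is sound for one arm, and SAP 4 does not carry the mislabel. The reply does not rescue Protocol 9.2.2, which attaches the limit to the common SD and justifies the bar by the pooled SD of a two-group comparison.

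A reader might go further and infer that 0.36 is a wrong or harmful threshold. The documents do not support that. SD = 2 is treated as known but comes from 15 people. Allowing for this at 38 df gives 2 × √F(0.95; 38, 14) = 3.015, and 1 / 3.015 = 0.33. At the other end, the 95th percentile of the observed SD pooled over four arms (76 df, true SD 2) is 2.26, and 1 / 2.26 = 0.44. So 0.36 lies inside a defensible range.

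Nor is the sample size in doubt: both documents say that it was set for administrative reasons, and neither claims power against control.

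**Conclusion.** The point holds as a mismatch between a number and the quantity it is said to describe, behind a decision threshold. With SD = 2 and a one-sided 95% limit, 2.74 belongs to 19 df. The SD pooled over a SET arm and control has a limit of 2.47, which implies 0.40. Separately, a confidence limit for the true SD is misused as a bound on the observed SD.

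The consequence is modest: about 4 percentage points on the chance that any of three ineffective doses passes, and between 4 and 5 on the chance that a dose at the MCID passes. Both differences rest on unadjusted change, a true SD of exactly 2 and no dropout. The planned estimate comes from a covariate-adjusted repeated-measures model, so they indicate scale and are not operating characteristics of the trial. The SD limits need only SD = 2 and normally distributed changes. The correction should be made, but nothing here shows that 0.36 is a bad bar.

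**What to change.** In Protocol 9.2.2 and SAP 4, take one of two routes.

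- **Correct the derivation.** Give 2.47 with 38 df as the limit for the SD pooled over a SET arm and control, with the bar of 0.40 that follows by the stated method, and state the df. This changes a pre-specified threshold, so it needs a dated amendment made without sight of results by arm. The bar becomes slightly stricter, by the amounts shown above.
- **Keep 0.36.** State it as a chosen, pre-specified bar, or as resting on a one-arm limit (19 df), and remove the claim that it follows from the common-SD limit. This costs only wording. It is preferable if results by arm may have been seen, which is possible because the unblinded statistician fits the primary model semi-annually (Protocol 9.4.6, SAP 12).

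On either route, reword the sentence so that a limit for the true SD is not presented as a bound on the observed one. Add one sentence to Protocol 9.4.2 and SAP 7 naming the denominator of the standardized mean difference at 3 months: which arms are pooled, and whether it is the SD of raw change or the model-based SD. The bar and the estimate should use the same SD.
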